### 7.3 DEVICE STORAGE

The size 23 mm Magna mitral valve inventory will be stored in a controlled, cool, dry and clean area. This area must be secure and only accessible to the Principal Investigator(s), his/her co-Investigators or approved designee. Only surgeons identified in the Clinical Study Agreement and Delegation of Authority Log on file may implant this investigational device.

### 7.4 DEVICE RETURN

The Principal Investigator(s) will be notified in writing upon termination of the study. All unused size 23 mm Magna mitral valve will be returned upon receipt of this notice. In the event that a device package is opened, but the device is not used, the Principal Investigator is to return the product. The Investigator's copy of the Device Accountability log must document any unused devices that have been returned. The valve should be placed in a container with a suitable histological fixative such as 10% formalin or 2% glutaraldehyde immediately and returned to Edwards. Refrigeration

is not necessary under these circumstances. Contact Edwards Clinical Research for additional instructions.

## **8 PROCEDURES AND METHODS**

### **8.1 ORIENTATION OF INVESTIGATIONAL SITE PERSONNEL**

Principal Investigator(s) and support staff will be trained by an Edwards Lifesciences representative on the use of the device, the Protocol, Case Report Forms, GCP and ICH Guidelines and other study documents as applicable. Training will be documented on a training form provided by Edwards Lifesciences, which all trainees must sign and date. In addition, a “Delegation of Authority Form” will be completed at each investigational site designating which individuals are allowed to perform specific study related tasks.

### **8.2 INFORMED CONSENT**

Subjects who are eligible for the study should be explained the following:

1. the background of the study;
2. the potential benefits and risks of the procedures involved;
3. study follow-up requirements

The subject should be given the opportunity and ample time to read and understand the Informed Consent in its entirety to make an informed decision. The subject must sign and date the institution’s Institutional Review Board (IRB) approved Informed Consent prior to participation or according to regulations regarding Informed Consent for subjects unable to sign a consent form. The Investigator or designee must sign and date the consent as well. Failure to provide written Informed Consent renders the subject ineligible for the study. [REDACTED]

### **8.3 SUBJECT SCREENING**

All patients admitted for mitral valve replacement should be screened for study eligibility. A Screening Log will be provided to the investigational sites to maintain a cumulative log of all screened patients admitted for mitral valve replacement. A member of the research team at the investigational site should review the subject's eligibility prior to enrolling potential subjects. If it is deemed that a subject is not eligible for participation in the study, a reason supporting the disqualification of the subject must be entered on the screening log. Any patients that are screen failures due to the need of mitral valve repair may be re-screened at a later time should mitral valve replacement be needed. Re-screened patients must be re-entered on the Screening Log. The Screening Log should be duly completed and is to be sent to the Sponsor on a regular basis.

#### 8.4 SUBJECT ENROLLMENT

All subjects who meet eligibility requirements will be asked to participate. A subject will be considered enrolled into the study and assigned a subject number after signing the informed consent.

#### 8.5 BASELINE – PRIOR TO PROCEDURE

A baseline evaluation is to be conducted within 1 month prior to device implant.

The baseline evaluation will include:

1. History and physical examination
2. Screening for clinical inclusion and exclusion criteria
3. Baseline blood studies (Complete blood count and Plasma Free Hemoglobin)
4. Baseline echocardiography per protocol \*\*
5. Baseline 12 lead electrocardiogram
6. NYHA Functional Class
7. Quality of Life Survey (EQ-5D)

\*\* Baseline echocardiography must be completed within 6 months of study procedure.

Baseline information, findings, and results to be recorded are identified in Table 3.

**Table 3: Baseline Evaluation**

General Information	Clinical Information	Blood Studies	Echocardiography
Subject ID Number Subject Initials Birth Date Subject Sex Physical Assessment	Cardiac Rhythm Cardiovascular Risk Factors Cardiovascular Conditions Non-Cardiovascular Conditions Previous Procedures / Interventions	Blood Draw Date White Blood Cell Count Red Blood Cell Count Hemoglobin Hematocrit Platelet Count Plasma Free Hemoglobin	Date of exam 2D measurements  Ejection fraction Mitral valve assessment  LVOT assessment Aortic Valve assessment  Other Variables  Left Ventricular Assessment 

Subjects who are enrolled in the study (signed an informed consent) but do not receive a device may be exited from the study and exempt from data collection after the baseline evaluation. The investigational site must retain the subject’s signed informed consent and all other source documents regarding the Baseline procedures. Verification that the subject(s) signed the informed consent will occur during the on-site monitoring visit.

### 8.6 PROCEDURE

The surgical technique employed will be that developed and perfected by the Investigator in his/her normal practice of cardiac surgery. The Magna mitral sizer must be used intra-operatively to confirm that the size 23 mm Magna mitral valve

 2-Dimensional measurements are Interventricular Septal thickness (IVS), Left Ventricular Internal Diameter in diastole (LVEDD), end diastolic Posterior Wall thickness (PW), Left Ventricular Internal Diameter in systole (LVESD), Left Atrium (LA), Left Ventricular Outflow Tract (LVOT)

 Mitral valve assessment includes the following parameters Mitral Valve Peak Flow Velocity (VmaxMV), Mean Pressure Gradient: Mitral Valve (MPG MV), Peak Pressure Gradient: Mitral Valve (PPG MV), Mitral Valve Time Velocity Integral (TVI MV), presence of Stenosis, presence and degree of Regurgitation

 Aortic valve assessment includes the following parameters Aortic Valve Peak Flow Velocity (VmaxAV), Mean Pressure Gradient: Aortic Valve (MPG AV), Aortic Valve Time Velocity Integral (TVI AV)

 Other variables includes the following parameters which are calculated by the echo machine Stroke Volume (SV), Cardiac Output (CO), Cardiac Index (CI), Effective Orifice Area: Mitral Valve (EOA MV)

 Left ventricular Assessment includes presence of wall motion abnormality, thrombi, pericardial effusion and other relevant clinical findings

can be implanted (TAD of valve is 27 mm). If the operator determines during the procedure that the subject is ineligible to receive the study valve, the subject will not be considered part of the study cohort and data after baseline evaluation will not be collected. Special attention should be given to proper orientation of the size 23 mm Magna mitral valve. Investigators are expected to be familiar with Precautions and Technique information described in the Instructions for Use [REDACTED] prior to use of the size 23 mm Magna mitral valve.

Procedural information, findings, results and size23mmMagna mitral valve identification information to be recorded is identified in Table 4.

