In order to further minimize risks, the valve will be implanted only by trained cardiac surgeons, familiar with mitral valve replacement. Qualified personnel from Edwards will provide training to the physicians and OR staff regarding the use of this valve and the details of the clinical protocol prior to enrollment of the first patient. During the clinical study, there are strict inclusion/exclusion criteria for patient participation developed in accordance with the risk analysis, valve size and intended use. In addition, a sizer for the 23 mm Magna mitral valve is provided. This sizer, like the

sizers for the Magna mitral valve sizes 25 through 33 mm, is marked for both size and EOA to provide clinically relevant information during surgery and to ensure correct sizing. If a patient who has been consented through the preoperative screening process is found, during the procedure, to require a different size valve, the patient will be terminated from the study and will receive the valve size most appropriate for their anatomy. Finally, all data will be reviewed by a Data Safety Monitoring Board at regular intervals throughout the study to ensure patient safety.

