## 10 ADVERSE EVENT REPORTING

All types of adverse events (AEs) will be reported by the Investigator and reviewed by the Sponsor in compliance with applicable regulations. Adverse event information will be collected from the point of implant. Adverse event information including but not limited to, a description event, date of onset, and relationship to device will be recorded on the CRF by the Investigator or research coordinator. Adverse events will be followed until they are adequately resolved or explained.

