### **ANALYSIS POPULATION**

The primary safety and effectiveness analyses will include all the implanted subjects. All the data collected up to the point of the explant or expirations will be included in the safety and effectiveness analyses.

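### Section 8.6 sets no cut-off for exclusion during surgery, so a study valve tried at the annulus and abandoned in the same operation can drop out of the early safety results

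*Combined protocol and SAP*

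**What the plan says.** All references are to the combined protocol and SAP.

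- **Enrolment (8.4).** "A subject will be considered enrolled into the study and assigned a subject number after signing the informed consent". Subjects are therefore in the study before surgery.
- **Exclusion in surgery (8.6).** The trigger is: "If the operator determines during the procedure that the subject is ineligible to receive the study valve". The consequence is: "the subject will not be considered part of the study cohort and data after baseline evaluation will not be collected".
- **Another size needed (3.2).** If this is found in surgery, "the patient will be terminated from the study and will receive the valve size most appropriate for their anatomy".
- **No device received (8.5, text after Table 3).** Such enrolled subjects "may be exited from the study and exempt from data collection after the baseline evaluation". This is permissive, whereas 8.6 is absolute.
- **Start of safety collection (10).** "Adverse event information will be collected from the point of implant".
- **Analysis population (11).** "The primary safety and effectiveness analyses will include all the implanted subjects".
- **Opened but unused valves (7.4).** "In the event that a device package is opened, but the device is not used, the Principal Investigator is to return the product". Section 7.2 has device disposition logged.

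Section 5 counts the sample as 15 to 20 implanted subjects. Section 11.1.1 defines the early rate as events within 30 days divided by subjects. No section defines an implanted subject or an attempted implant.

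**The concern.** The rule in 8.6 can be invoked at any point in the operation. It does not separate a subject excluded at sizing, who was never exposed to the study valve, from one in whom the valve was seated or sutured and then given up for poor fit, leak or obstruction. Exclusion in the second case follows exposure and may depend on how the device behaved.

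This matters for a new smallest size. Section 3.1.2 lists harms that can arise while the valve is being placed, including distortion at implant, leaflet entrapment and perforation of the ventricle by the stent posts. Section 3.2 treats oversizing as something to avoid. Because the sample is counted in implants, another subject can take the place of an abandoned attempt and the total shows nothing. The resulting rates are to be set beside Protocol 98-1 (Section 11) and to support a premarket supplement (Section 4).

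**Working it through.** The study is descriptive. It states no power, alpha or abandonment rate, so there is no figure of the plan's own to reproduce. The check has two parts.

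**1. Where does a valve tried and abandoned in the same operation go?**

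| Possible route | Does it recover the case? |
|---|---|
| Procedure form, Table 4 (has a field for intraoperative events) | Not if 8.6 is applied, since collection stops after baseline |
| Adverse event collection (10) | Starts at implant, which is undefined |
| Explant endpoint (11.1.1, Table 8) | Counts a valve implanted and later removed; removal in the same operation is not clearly assigned |
| Unanticipated device effects (10.3) | Not limited to implanted subjects, but leaves out effects already identified in nature, severity and incidence, so the harms listed in 3.1.2 would generally not qualify |
| Accountability log and device return (7.2, 7.4) | Leaves an inventory trace; nothing links it to the safety tables |
| Data Monitoring Committee (13.1) | Reviews events that were reported |

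Recovery is partial. No route clearly returns the case to the early rates.

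**2. How much could it matter?**

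Inputs: n = 15 or 20 implanted (Section 5); early rate = events / subjects (Section 11.1.1). Assumptions: no reported events, and k uncounted attempts, each with an event.

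Rate with the attempts counted = k / (n + k). Exact (Clopper-Pearson) 95% limits for x events in N subjects: lower = Beta quantile at 0.025 with parameters (x, N − x + 1), upper = Beta quantile at 0.975 with parameters (x + 1, N − x). For x = 0 the lower limit is 0 and the upper is 1 − 0.025^(1/N).

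| k | 15 implanted | 20 implanted |
|---|---|---|
| 0 | 0/15 = 0% (0 to 21.8%) | 0/20 = 0% (0 to 16.8%) |
| 1 | 1/16 = 6.25% (0.2 to 30.2%) | 1/21 = 4.8% (0.1 to 23.8%) |
| 2 | 2/17 = 11.8% (1.5 to 36.4%) | 2/22 = 9.1% (1.1 to 29.2%) |
| 3 | 3/18 = 16.7% (3.6 to 41.4%) | 3/23 = 13.0% (2.8 to 33.6%) |

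The chance of at least one exclusion in m attempts, at an assumed exclusion rate q per attempt, is 1 − (1 − q)^m:

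| q | m = 15 | m = 20 |
|---|---|---|
| 2% | 26% | 33% |
| 5% | 54% | 64% |
| 10% | 79% | 88% |
| 20% | 96% | 99% |

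The second table counts exclusions of any kind. An event is lost only if the excluded subject was exposed and also had one.

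**Direction.** The shift need not be upward. If one implanted subject of 20 has an event and one excluded subject has none, counting the attempt moves 1/20 = 5.0% to 1/21 = 4.8%.

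**The case against.** The strongest reply is that 8.6 concerns sizing. The sentence directly follows the instruction to use the sizer in surgery, its trigger is a judgement about eligibility to receive the valve, and 3.2 and 8.5 describe the parallel cases of a different size and of no device received. None of them describes a valve sewn in and then taken out. That is very likely the intent, and leaving out subjects never exposed to the device is sound. It does not settle the point, because the text is not limited to sizing.

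The case report forms and Instructions for Use are not available in the public text, so the procedure form may record attempts. Even so, 8.6 as written ends collection for these subjects.

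A reader might go further than the documents allow in four ways:

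- **That no data are kept.** Baseline data, consent and source documents are retained (8.5), as are device records.
- **That nothing recovers an abandoned attempt.** The routes set out in the working recover some cases.
- **That every early rate is biased favourably.** Thrombosis or structural deterioration of the study valve cannot occur later in someone who leaves surgery with another prosthesis, so counting that subject can lower such a rate. An early death under another prosthesis also raises a question of attribution.
- **That implant success is overstated.** It is not an endpoint. Section 8.7.2 mentions procedural success once, without a definition.

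**Conclusion.** The concern holds as a gap in the rule. The plan permits a study valve tried at the annulus and abandoned in the same operation to be treated as ineligibility, so that its intraoperative and early events can be lost. For events such as death, hemorrhage or reoperation, the early rates could then be too favourable. For other endpoints the direction depends on the case.

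With one such attempt and one event, a rate reported as zero would be 6.25% with 15 implants or 4.8% with 20. The intervals overlap widely, so in sampling terms the shift is modest. In a descriptive study this small, however, the difference between no event and one event is much of what a reader takes away. These sizes rest on an assumed number of uncounted attempts, each with an event. The documents do not show that this has happened or how often it would. The change is worth making because it is cheap and removes the ambiguity.

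**What to change.** 1. In 8.6, confine the exclusion to subjects excluded before the study valve is brought to the annulus.
2. Define an implanted subject, and define an attempted-implant set: every subject whose study valve was brought to or placed in the annulus.
3. For that set, collect and report intraoperative and 30-day adverse events and vital status, beside the same rates for the implanted set. Amend Section 10 so that collection starts early enough to cover these subjects.
4. State whether removal in the same operation counts as an explant or as an attempted implant only.
5. Add a flow table from consent to implant with the reason for each exclusion. List opened-but-unused valves separately, since opening a package is handling and not exposure of the patient.
6. Reconcile the permissive wording in 8.5 with the absolute wording in 8.6.
7. Keep the implanted set for the late and hemodynamic analyses.

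The cost is protocol and SAP wording and early follow-up of a few extra subjects. Some early rates may look slightly less favourable.

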**Table 4: Procedural Information**

General Information	Clinical Information
Subject ID Number	Etiology
Subject Initials	Surgical approach
Date of Procedure	Diagnosis for replacement
Implanting surgeon	Valve implant
Device serial number	Condition of the annulus
	Debridement procedure
	Condition of the valve being replaced
	Preservation of Subvalvular apparatus
	Concomitant procedures
	Intraoperative Adverse Events

## 8.7 POST-PROCEDURE

### 8.7.1 POST-PROCEDURE CARE

Bioprosthetic heart valve recipients should be maintained on anticoagulant therapy (except when contraindicated) during the initial healing stages after implant, approximately 2 to 3 months. Anticoagulants should then be discontinued over a period of 10 days, except in those patients for whom indefinite anticoagulant protection is indicated, i.e., in the absence of sinus rhythm and in patients with a dilated left atrium, calcification of the atrial wall, or history of previous atrial

thrombus. However, the appropriate anticoagulation therapy must be determined on an individual basis.

#### 8.7.2 DISCHARGE

At discharge, the Investigator or designee will provide the subject with an Implant Data Card [REDACTED]. The Implant Data Card must be completed with the required information (i.e., the name of the Investigator, the contact information and the name of the investigational site). The Investigator or designee should also obtain from the device package two stickers with the implanted Magna mitral serial number and affix one sticker on the Implant Data Card and the second sticker on the front page of the subject's operations notes. In addition, the Investigator or designee must explain to the subject the purpose of this Implant Data Card.

Documentation of alternate contact information such as referring physicians, and relatives should be collected in the event that the subject cannot be reached at his/her primary residence. The research coordinator of the study should record any planned extended or seasonal absence from the subject's place of residence and take into consideration when planning follow up visits. A clinical evaluation including echocardiography of the subject will be performed at discharge from the hospital or within 30 days from implant, whichever comes first. Echocardiography will be sent to the Core Lab for analysis [REDACTED]. [REDACTED]. Medical information, findings, and results information to be recorded is identified in Table 5.

**Table 5: Discharge Evaluation**

General Information	Clinical Information	Echocardiography
Subject ID Number Subject Initials	Subject status Cardiac Rhythm Physical Assessment Coagulation Profile Antithromboembolic therapy Adverse Events	Date of exam 2D measurements  Ejection fraction Mitral valve assessment  LVOT assessment Aortic Valve assessment  Other Variables  Left Ventricular Assessment 

DISCHARGE ECHCARDIOGRAPHY

Subjects, who are not discharged within 10 days post procedure must have an echocardiogram to further assess placement and performance of the bioprosthesis. This echocardiogram is required to complete the evaluation of procedural success. Those subjects will not require an additional echocardiogram at discharge.

8.7.3 FOLLOW-UP ASSESSMENTS

Post-procedure clinical evaluation will be performed on all subjects at 6 months post procedure, 1 year post procedure, and annually thereafter until 5 years post procedure, adhering to the visit windows in Table 6.

**Table 6: Visit windows**

Interval	Window
6 months post procedure	3-6 months
1 year post procedure	± 1 month of annual visit
Subsequent annual post procedure	± 2 month of annual visit

During the clinical evaluation of the subject, medical information, findings, and results will be recorded. Blood will be drawn at 6 months post procedure, 1 year

 2-Dimensional measurements are Interventricular Septal thickness (IVS), Left Ventricular Internal Diameter in diastole (LVEDD), end diastolic Posterior Wall thickness (PW), Left Ventricular Internal Diameter in systole (LVESD), Left Atrium (LA), Left Ventricular Outflow Tract (LVOT)

 Mitral valve assessment includes the following parameters Mitral Valve Peak Flow Velocity (VmaxMV), Mean Pressure Gradient: Mitral Valve (MPG MV), Peak Pressure Gradient: Mitral Valve (PPG MV), Mitral Valve Time Velocity Integral (TVI MV), presence of Stenosis, presence and degree of Regurgitation

 Aortic valve assessment includes the following parameters Aortic Valve Peak Flow Velocity (VmaxAV), Mean Pressure Gradient: Aortic Valve (MPG AV), Aortic Valve Time Velocity Integral (TVI AV)

 Other variables includes the following parameters which are calculated by the echo machine Stroke Volume (SV), Cardiac Output (CO), Cardiac Index (CI), Effective Orifice Area: Mitral Valve (EOA MV)

 Left ventricular Assessment includes presence of wall motion abnormality, thrombi, pericardial effusion and other relevant clinical findings

post procedure, and annually thereafter until 5 years post procedure. A Quality of Life survey will be required at 6 month and 12 month post procedure. Echocardiography will be required 6 months, 1 year, 2 years, 3 years, 4 years, and 5 years post procedure and will be evaluated by an independent Core Lab. Information to be recorded is identified in Table 7.

**Table 7: Follow-up Evaluation**

General Information	Clinical Information	Blood Studies	Echocardiography
Subject ID Number Subject Initials Date of Evaluation Visit Status	Patient Status Physical Assessment Cardiac Rhythm NYHA Functional Class Antithromboembolic therapy Adverse Events	Blood Draw Date White Blood Cell Count Red Blood Cell Count Hemoglobin Hematocrit Platelet Count Plasma Free Hemoglobin	Date of exam 2D measurements  Ejection fraction Mitral valve assessment  LVOT assessment Aortic Valve assessment  Other Variables  Left Ventricular Assessment 

At each postoperative assessment, the Investigator(s) will need to determine the subject's availability for future follow-up. If any subject needs to be seen at a time other than a regularly scheduled follow-up visit, the same information as described above will be documented by the Investigator and indicated as an interim visit. Follow-up information obtained by physicians outside of the investigational site should be obtained by the Investigator.

 2-Dimensional measurements are Interventricular Septal thickness (IVS), Left Ventricular Internal Diameter in diastole (LVEDD), end diastolic Posterior Wall thickness (PW), Left Ventricular Internal Diameter in systole (LVESD), Left Atrium (LA), Left Ventricular Outflow Tract (LVOT)

 Mitral valve assessment includes the following parameters Mitral Valve Peak Flow Velocity (VmaxMV), Mean Pressure Gradient: Mitral Valve (MPG MV), Peak Pressure Gradient: Mitral Valve (PPG MV), Mitral Valve Time Velocity Integral (TVI MV), presence of Stenosis, presence and degree of Regurgitation

 Aortic valve assessment includes the following parameters Aortic Valve Peak Flow Velocity (VmaxAV), Mean Pressure Gradient: Aortic Valve (MPG AV), Aortic Valve Time Velocity Integral (TVI AV)

 Other variables includes the following parameters which are calculated by the echo machine Stroke Volume (SV), Cardiac Output (CO), Cardiac Index (CI), Effective Orifice Area: Mitral Valve (EOA MV)

 Left ventricular Assessment includes presence of wall motion abnormality, thrombi, pericardial effusion and other relevant clinical findings

The Investigator(s) will make every attempt to follow the subjects and will document the information gathered during the follow-up visits on the Case Report Forms [REDACTED]. Subjects will be informed by the Investigator(s) about the importance of returning for scheduled follow-up visits even if they are not having any problems. Subjects will also be directed to communicate any address or telephone number changes.

